#### **8.1.2 Randomization and Stratification**

This study will not require randomization or stratification.

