**Secondary Efficacy Endpoints**

The number and percentage of patients in each response category (CR, partial response, SD, disease progression, ORR, CBR-24, and CBR) will be tabulated for each cohort.

PFS is defined as the time from the date of first MLN0128 administration to the date of first documentation of disease progression or death. OS is defined as the time from the date of first MLN0128 administration to the date of death. PFS and OS will be analyzed using Kaplan-Meier methodology for each cohort.

Waterfall plots of the best percentage of change from Baseline in the sum of the longest diameter (SLD) of the target lesion will be generated for each cohort.

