7.8.2 Secondary Efficacy Endpoint(s)

Phase 2

Clinical benefit rate at 24 weeks (CBR-24)

The CBR-24 is defined as the proportion of patients who achieve CR or partial response of any duration, or have SD at 24 weeks.

The number and percentage of patients achieving CBR-24 will be summarized by cohort and combination partner (Exemestane or Fulvestrant) within each cohort. The estimate of the CBR-24 will be presented with a 2-sided 95% exact binomial confidence interval. The CBR-24 will be determined based on both unconfirmed and confirmed best overall response (see Section 7.8.3 Additional Efficacy Endpoints for definitions) for the response-evaluable population.

SD for at least 24 weeks is a subset of SD, only calculated for those patients with a best response of SD. It is defined as SD at the end of Cycle 2, Cycle 4, and Cycle 6 (see exception below).

CBR at 24 weeks (unconfirmed) is defined as the number of patients who achieve CR or PR at any time or have SD for at least 24 weeks.

CBR at 24 weeks (confirmed) is defined as the number of patients who achieve confirmed CR or confirmed PR at any time or have SD for at least 24 weeks or meet the following criteria:

Overall response at end of Cycle 2	Overall response at end of Cycle 4	Overall Response at the end of Cycle 6
CR/PR (unconfirmed)	SD	SD
SD	CR/PR (unconfirmed)	SD
SD	SD	CR/PR (unconfirmed)

Overall response rate (ORR)

The ORR is defined as the proportion of patients with a best response of CR or partial response. The number and percentage of patients achieving an ORR will be summarized by cohort and combination partner (Exemestane or Fulvestrant) within each cohort. The estimate of the ORR will be presented with a 2-sided 95% exact binomial confidence interval. The ORR will be determined based on both unconfirmed and confirmed best overall response (see Section 7.8.3 Additional Efficacy Endpoints for definitions) for the response-evaluable population.

Progression-free survival (PFS)

Progression-free survival is defined as the time from the date of first MLN0128 administration to the date of first documentation of disease progression or death due to any cause, whichever occurs first. Progression is based on the investigator response assessment per RECIST 1.1 criteria.

PFS in months is defined as:

(earliest date of progression or death – date of first dose of MLN0128 + 1)/30.4375

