In the event of progression, the date of progression is defined as the earliest date among target lesions, non-target and new lesions dates at that particular visit. For a patient whose disease has not progressed and is last known to be alive, PFS will be censored at the last response assessment that is SD or better.

The approach for handling of missing response assessments and censoring is presented in [Table 7.a](#).

Table 7.a Handling of Missing Response Assessment and Censoring

Situation	Date of Progression or Censoring	Outcome
No baseline tumor assessment	Randomization	Censored
No post baseline tumor assessment and no death	Randomization	Censored
Disease progression documented between scheduled visits	Date of first documented disease progression	Progressed
Disease progression documented subsequent to missing 2 or more adequate tumor assessments	Date of first documented disease progression	Progressed
No documented disease progression or no death	Date of last adequate assessment	Censored
Alternate subsequent therapy started prior to disease progression	Date of last adequate assessment prior to the start of subsequent therapy	Censored
Death without progression and without subsequent anti-cancer therapy	Date of death	Progressed
Adequate Assessment: investigator response assessment other than Unable to Assess, unknown or missing (i.e. CR, PR, SD or PD).		

PFS Analysis

The Kaplan-Meier method will be used to analyze the distribution of PFS for the Safety Population. Kaplan-Meier survival curves, the 25th, 50th (median), and 75th percentiles, along with associated 2-sided 95% confidence intervals (CIs) based on Brookmeyer and Crowley, and Kaplan-Meier estimates with 95% CIs at 6, 12 and 18 and 24 months will be presented.

The source of PFS (death or progressive disease) and the status of subjects who are censored in the PFS Kaplan-Meier analysis [no post baseline tumor assessment and no death, on-study (on treatment, in follow-up), Lost to follow-up, and received subsequent anti-cancer therapy] will be tabulated.

PFS will be summarized by cohort and combination partner (Exemestane or Fulvestrant) within each cohort.

Overall survival (OS)

Overall survival in months is defined as: (date of death – date of first dose of MLN0128 + 1) / 30.4375. Patients without documentation of death at the time of analysis will be censored at the

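### SAP Table 7.a contradicts the PFS definition: row 5 prints 'or' where 'and' is needed, row 1 can censor a death, and rows 1 and 2 censor at a randomization date that does not exist

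*SAP*

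**What the plan says.** The definition is consistent across the two documents. Protocol 8.1.6: "PFS is defined as the time from the date of first MLN0128 administration to the date of first documentation of disease progression or death". SAP 7.8.2 uses the same origin and runs "to the date of first documentation of disease progression or death due to any cause, whichever occurs first". The SAP then gives its censoring rule in prose: "For a patient whose disease has not progressed and is last known to be alive, PFS will be censored at the last response assessment", provided that assessment shows SD or better.

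The SAP next refers the reader to Table 7.a for missing assessments and censoring. The rows are not numbered; counted from the top they are:

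| Row | Situation | Handling |
|---|---|---|
| 1 | "No baseline tumor assessment" | Censored at randomization |
| 2 | No assessment after baseline, and alive | Censored at randomization |
| 3 | Progression found between scheduled visits | Event |
| 4 | Progression found after at least two missed assessments | Event |
| 5 | "No documented disease progression or no death" | Censored at last adequate assessment |
| 6 | New therapy before progression | Censored at last adequate assessment before it |
| 7 | "Death without progression and without subsequent anti-cancer therapy" | Event at date of death |

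A footnote counts CR, PR, SD and PD all as adequate assessments. Protocol 8.1.2 states: "This study will not require randomization or stratification".

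**The concern.** A censoring table is what a programmer codes from. Row 5 joins two negatives with *or*, so a patient needs to meet only one of them to be censored. A living patient with documented progression meets the second; a patient who dies without progression meets the first. Both are PFS events by definition. If the row were coded as printed, real events would leave the Kaplan-Meier analysis and median PFS would be overstated in both cohorts.

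Row 1 does not exclude patients who died, although row 2 does. PFS is analysed in the Safety Population (anyone dosed), so a patient without a baseline assessment stays in the analysis and her death would be censored. The censoring date in rows 1 and 2 cannot be computed, because nobody is randomized.

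**Working it through.** The plan gives no event count, power or median for PFS, so there is no figure of its own to reproduce. The main check is logical.

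**Row 5 against the definition.** There are four possible states:

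| Documented progression | Died | Definition | Row 5 with *or* | Row 5 with *and* |
|---|---|---|---|---|
| No | No | Censor | Censor | Censor |
| No | Yes | Event | **Censor** | Event |
| Yes | No | Event | **Censor** | Event |
| Yes | Yes | Event | Event | Event |

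As printed, row 5 agrees with the definition in 2 of 4 states; with *and* it agrees in 4 of 4. The second line also conflicts with row 7 whenever no new therapy was given. In the third line, because PD is an adequate assessment, the patient could be censored on the progression date itself.

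**Rows 1 and 2.** The stated origin is first MLN0128 dose. If that date replaces randomization, the SAP formula gives (0 + 1)/30.4375 = 0.033 months, that is, 1 day. Row 1 still censors a death until its condition is narrowed.

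**Illustration of literal coding.** Every input here is an assumption, and row 5 is applied to all patients, overriding rows 3, 4 and 7.

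- Let *a* be the share of PFS events that are deaths without progression (5% to 20%), *b* the share of progressors alive at cut-off (30% to 60%), and *m* the true median of an exponential PFS.
- Literal row 5 keeps a share r = (1 − a)(1 − b) of events. If r does not depend on event time, the event hazard is multiplied by r and the Kaplan-Meier median becomes m/r.
- r lies between 0.95 × 0.70 = 0.665 and 0.80 × 0.40 = 0.32, so the median is multiplied by 1/0.665 = 1.5 to 1/0.32 = 3.1.
- For m = 2, 4 and 6 months this gives 3.0 to 6.3, 6.0 to 12.5, and 9.0 to 18.8 months. A simulation of 200,000 patients with follow-up uniform on 12 to 30 months gives 3.0 to 6.3, 6.0 to 12.4, and 9.0 to 18.6.

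**Second illustration, letting r fall with event time.** Take m = 4 months, all events progressions, exponential post-progression survival with median s, and cut-off at 18 months. A progression at time u stays an event only if death follows by 18 months, with probability 1 − 2^(−(18−u)/s). The median t then solves t − (s/ln 2) × 2^(−18/s) × (2^(t/s) − 1) = 4.

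- s = 12: the multiplier is 17.31 × 0.3536 = 6.12, and 7.1 − 6.12 × 0.507 = 4.0, so t is about 7.1. About 51% of progression events are kept.
- s = 18: the multiplier is 25.97 × 0.5 = 12.98, and 10.4 − 12.98 × 0.4925 = 4.0, so t is about 10.4. About 39% are kept.
- If rows 3 and 4 are honoured and cover 20% to 40% of progressions (also assumed), the multiplier shrinks by a factor of 0.8 to 0.6 and the median falls to about 5.3 (s = 12, 40%) to 7.5 (s = 18, 20%).

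**The case against.** The strongest reply is that the SAP itself rules out the literal reading of row 5. The sentence above the table uses *and*. Rows 3 and 4 make progression an event without requiring death, and row 7 makes a death without progression an event. The SAP also plans to tabulate whether each PFS event was a death or a progression; if every event needed both, no event could have death as its source. Its listed statuses for censored patients include neither progressed-and-alive nor died-without-progression. All of this stands: *and* was clearly intended.

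A reader might infer three stronger things that the documents do not support.

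- That median PFS will be biased. This follows only if row 5 is coded as printed, and such output would not fit the planned tables.
- That the table leaves out the commonest event, progression at a scheduled visit. The table deals with missing assessments and censoring; ordinary progression is covered by the PFS definition and by the sentence on dating a progression. A separate row is optional.
- That a key endpoint is at risk. Neither document calls PFS key; it is one of seven listed secondary endpoints, protocol 8.1.6 makes the efficacy analysis descriptive, and no PFS test is planned.

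It is also fair that row 1 should be nearly empty: phase 2 entry requires measurable disease or bone lesions, and imaging is required within 4 weeks before first dose.

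What the reply does not remove is the contradiction. The SAP names the table as its approach to censoring, and nothing states that the text prevails over the table. The row 1 and randomization errors do not depend on how row 5 is read.

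**Conclusion.** Table 7.a is wrong as written on three points: *or* in row 5, no exclusion of deaths in row 1, and a non-existent censoring date in rows 1 and 2. The row 5 error is most likely a slip, and its intended rule is recoverable from the same section.

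If row 5 is read as intended, it does not shift PFS at all. If it were coded literally, the assumed scenarios multiply the median by 1.5 to 3.1, with a smaller shift if rows 3 and 4 take precedence. These are worst-case illustrations, not predictions: the documents give no PFS assumptions, and the figures rest on exponential times and the assumed shares above. Rows 1 and 2 should affect few patients. The primary endpoint CBR-16, the sample size and the futility rules do not use this table and are unaffected.

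The censoring of patients who start new therapy (rows 6 and 7) is a recognised convention and is not part of this point.

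**What to change.** In SAP Table 7.a:

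1. Row 5: change *or* to *and*, so that only a patient with neither documented progression nor death is censored there.
2. Rows 1 and 2: replace randomization by the date of first MLN0128 dose.
3. Row 1: add the condition that the patient has not died, so that a death without new therapy falls under row 7.

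Optionally, add a row making progression at a scheduled visit an event on its first documented date. This only restates what the text already says.

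The cost is a few wording edits in one table. No new data are needed, and no clinical rule or sample size changes.

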7.8.3 Additional Efficacy Endpoint(s)

Best Overall Response

Best Overall Response (unconfirmed): The best response after the first dose of study drug until subsequent therapy ordered from best to worst: Complete Response, Partial Response, Stable Disease, Progressive Disease. The best response can also be Unable to Assess, Unknown, or No assessment performed if this is the only investigator assessment of objective response available for the patient.

Best Overall Response (confirmed): The best response after the first dose of study drug until subsequent therapy ordered from best to worst: Complete Response, Partial Response, Stable Disease, Progressive Disease. The best response can also be Unable to Assess, Unknown, or No assessment performed if this is the only investigator assessment of objective response available for the patient.

Complete or partial responses may be claimed as best response only if the criteria for each are met at a subsequent time point. For the best overall response (confirmed), the confirmation derivation rules will be as described in the following table.

Confirmation Derivation Rules		
Overall response 1 st time point	Overall response subsequent time point	BEST overall response
CR	PR	PR
CR	SD	SD
CR	PD	SD
CR	NE	SD
PR	CR	PR
PR	PR	PR
PR	SD	SD
PR	PD	SD
PR	NE	SD
NE	NE	NE

Note: No adjustment for minimum criteria for SD is needed as the first protocol scan is at the end of cycle 2, approximately 8 weeks from first dose.

The number and percentage of patients in each response category (CR, PR, SD, SD-16, SD-24, Progressive Disease, Unable to Assess, Unknown, or no post baseline response assessment) will be summarized by cohort and combination partner (Exemestane or Fulvestrant) within each cohort.

Duration of Response (DOR)

The duration of objective response will be calculated for those patients with a best response of CR or PR, and is defined as the number of days from the start date of CR, or PR (whichever response is achieved first) until progressive disease or until the last response assessment if there is no progressive disease. For phase 2 the Kaplan-Meier method will be used to analyze the DOR. Kaplan-Meier survival curves, the 25th, 50th (median), and 75th percentiles, along with associated 2-sided 95% confidence intervals (CIs) based on Brookmeyer and Crowley will be presented.

Duration of Stable Disease

The duration of stable disease will be calculated for those patients with a best response of SD. The duration of SD is the number of days from cycle 1 day 1 until progressive disease or until the last response assessment if there is no progressive disease (listing).

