Tests and procedures should be performed on schedule, but occasional changes are allowable (±2 days) with permission from the medical monitor for holidays, vacations, and other administrative reasons. **If extenuating circumstances prevent a patient from beginning treatment or completing a scheduled procedure or assessment within this time, the patient may continue the study only with the written permission of the project clinician.**

aPTT=activated partial thromboplastin time, C=cycle, CT=computed tomography, CCI ECHO=echocardiogram, ECG=electrocardiogram,

	Screening (a)	TREATMENT CYCLES										EOT/ ET (b)	PFSFU /OSFU
		Cycle 1		Cycle 2			Cycle 3	Cycle 4		Cycles 5 and Beyond			
		Day 1	Day 15 (±2 Days)	Day 1	Day 15 (±2 Days)	Day 28 (±2 Days)	Day 1	Day 1	Day 28 (±2 Days)	Day 1	Day 28 (±2 Days)		

ECOG=Eastern Cooperative Oncology Group, eCRF=electronic case report form, EOT=End of Treatment (visit), ET=Early Termination, HbA1c=glycosylated hemoglobin, ICF=informed consent form, IM=intramuscular(ly), INR=international normalized ratio, mo=months, MRI=magnetic resonance imaging, MUGA=multiple gated acquisition (scan), OS=overall survival, OSFU=overall survival follow-up, PFS=progression-free survival, PFSFU=progression-free survival follow-up, PK=pharmacokinetic(s), PT=prothrombin time, Q=every, QD=once daily, RECIST=Response Evaluation Criteria in Solid Tumors, SmPC=Summary of Product Characteristics, USPI=United States Prescribing Information, X#=the number of samples required (eg, 2 samples=X2).

- (a) Screening assessments are performed within 28 days before the Cycle 1 Day 1 MLN0128 dose. Screening assessments performed no more than 3 days before Day 1 will qualify as baseline assessments and need not be repeated, unless otherwise specified.
- (b) Patients will attend an EOT/ET visit 30 to 40 days after receiving their last dose of MLN0128 or at the start of subsequent anticancer therapy, at which time patients will enter posttreatment follow-up. If subsequent anticancer therapy is required before 30 days after the last dose, the EOT/ET visit should be conducted before the initiation of subsequent anticancer therapy.
- (c) For patients enrolling into phase 2 who have measurable disease and are undergoing CT scans (rather than MRIs) for tumor assessment, the most recent CT scan performed before the baseline CT scan for this study will be collected, if available. See Section 7.4.3.

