- (d) Vital sign measurements include blood pressure (diastolic and systolic), heart rate, and temperature.
- (e) Single, 12-lead ECGs will be collected according to the schedule presented in the [Phase 1b Pharmacokinetic and ECG Sample Breakdown](#) and the [Phase 2 Pharmacokinetic and ECG Sample Breakdown](#) table. When the timing of an ECG coincides with blood samples for PK, the ECG should be completed first.
- (f) Contrast-enhanced imaging CT or MRI of the chest, abdomen, and pelvis must be obtained at baseline within 4 weeks before the first dose of MLN0128. Unless contraindicated, such contrast-enhanced imaging CT or MRI scans will be obtained every 2 cycles from Cycle 2 through Cycle 6 (ie, Cycle 2 Day 28, Cycle 4 Day 28, and Cycle 6 Day 28) and then every 3 cycles thereafter (ie, Cycle 9 Day 28, Cycle 12 Day 28, Cycle 15 Day 28, etc). A confirmatory scan should be performed at approximately 4 weeks from the previous scan for all patients with a complete or partial response. For those patients who have documented radiographic disease progression, CT or MRI scans are not required at the EOT visit. The same imaging modality (CT or MRI) should be used throughout the study.
- (g) After EOT, patients will be followed for PFS and OS; see Section 7.10 for more details. For those patients who discontinue MLN0128 for any reason other than radiographic disease progression, contrast-enhanced imaging CT or MRI scans should be completed to further assess disease progression (per RECIST, version 1.1).
- (h) Including serious pretreatment events; see Section 9.1.1.
- (i) Exemestane or fulvestrant should be administered according to the USPI or SmPC and according to the dose administered during previous treatment.
- (j) May be assessed up to 24 hours before the study visit.
- (k) For screening, creatinine clearance must be  $\geq 50$  mL/min based either on Cockcroft-Gault estimate or based on a 12- or 24-hour urine collection.
- (l) Coagulation assessment is required for all patients at times specified in the [Schedule of Events](#). When a tumor biopsy is required, coagulation assessment is required within 24 hours before obtaining the tumor biopsy. See Section 7.4.19 for additional information regarding tumor biopsy.
- (m) Fasting serum glucose will be measured in the clinic. Patients are required to fast overnight (nothing except water and/or medications after midnight or for a

	Screening (a)	TREATMENT CYCLES										EOT/ ET (b)	PFSFU /OSFU

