**MLN0128****Clinical Study Protocol C31001 Amendment 6, EudraCT: 2014-001921-34**

response for each patient will be derived programmatically from among the reported responses at the end of Cycle 4 and for the entire treatment period.

Data listings will present the tumor measurements on contrast-enhanced CT or MRI (including changes from Baseline) scans, disease response category (eg, CR, partial response, and SD), and other endpoints as appropriate.

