4.4 Study Design

This is a phase 1b/2 study of the safety and efficacy of MLN0128 in combination with exemestane or fulvestrant therapy in women with ER+/HER2- advanced or metastatic breast cancer that has progressed on treatment with everolimus in combination with exemestane (any country) or fulvestrant (US only). Patients enrolled in this study will continue taking the same

prior therapy (either exemestane or fulvestrant) at their established dose, in combination with MLN0128.

Eligibility will be determined during the Screening period, which may last for up to 28 days before the Cycle 1, Day 1 visit. Patients who meet all eligibility criteria and provide written informed consent will be enrolled in this study. MLN0128 will be administered in 28-day treatment cycles.

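### The SAP sets no minimum duration for stable disease because the first scheduled scan is at week 8, but its best-response rule also admits earlier, off-schedule scans

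*SAP*

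**What the plan says.** SAP 7.8.3 closes its best-response rules with this remark: "No adjustment for minimum criteria for SD is needed as the first protocol scan is at the end of cycle 2, approximately 8 weeks". The note treats a minimum criterion for SD as something that exists and that the scan calendar already satisfies. It gives no number of days.

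The same section defines best overall response, confirmed and unconfirmed, as "The best response after the first dose of study drug until subsequent therapy ordered from best to worst". It sets no earliest day and does not restrict the rule to scheduled scans. Of best overall response, Protocol 8.1.6 says that the "response for each patient will be derived programmatically from among the reported responses at the end of Cycle 4 and for the entire treatment period".

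On scan timing, the radiographic row of the Protocol's Schedule of Events marks Screening, Day 28 of Cycles 2 and 4, later Day 28 visits, and three-monthly follow-up. Its end-of-treatment (EOT) cell is blank. Footnote (f) nevertheless says: "For those patients who have documented radiographic disease progression, CT or MRI scans are not required at the EOT visit". Footnote (g) says that patients who stop MLN0128 for any other reason than radiographic progression should be scanned. On the visit itself, footnote (b) says: "Patients will attend an EOT/ET visit 30 to 40 days after receiving their last dose of MLN0128 or at the start of subsequent anticancer therapy".

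**The concern.** The reason given for dropping the check covers one set of scans, and the rule it supports uses a wider set. A patient whose drug is stopped during Cycle 1 for toxicity, without progression, may be scanned around her EOT visit. If that scan shows no change, the rule as written gives her a best response of SD, although she was observed for less than the interval on which the note relies.

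She also stays in the table. The response-evaluable population (Protocol 8.1.3, SAP 7.2.2) needs only one dose and measurable disease at baseline, so an early stopper is counted and not replaced. How she is classified therefore affects the SD row of the response-category table, which is planned by cohort and by combination partner. It also puts short intervals into the listing of SD duration. Any error goes one way, towards more SD.

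The confirmation table has the same gap. It turns a CR or PR followed by SD, PD or a non-evaluable assessment into SD, with no condition on when any of these assessments took place.

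**Working it through.** **1. The SAP's own figure.** Inputs: "MLN0128 will be administered in 28-day treatment cycles" (SAP 4.4); first on-treatment scan at Cycle 2 Day 28, with a window of 2 days either side (Schedule of Events); first dose is Study Day 1 (SAP 7.1.2).

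- Cycle 2 Day 28 = 28 + 28 = Study Day 56; 56/7 = 8.0 weeks. The SAP's figure is reproduced.
- Window: Study Days 54 to 58. The earliest compliant scan is on Study Day 54, which is 54 − 1 = 53 days after first dose.

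**2. When an EOT scan would fall.** Let L be the study day of the last dose. With the visit 30 to 40 days later, a scan at that visit falls between L + 30 and L + 40.

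- Always before Day 54: L + 40 ≤ 53, so L ≤ 13.
- Possibly before Day 54: L + 30 ≤ 53, so L ≤ 23. This adds last doses on Days 14 to 23.
- If new anticancer therapy brings the visit forward, a later last dose can also qualify. Footnote (b) asks for the visit before that therapy starts, so a scan done there stays inside the SAP's best-response window.

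The result depends on the cut-off:

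| Cut-off | Always before it | Can be before it |
|---|---|---|
| Study Day 56 (nominal scan day) | L ≤ 15 | L ≤ 25 |
| Study Day 54 (window opens) | L ≤ 13 | L ≤ 23 |
| Study Day 42 (6 weeks, an assumption) | L ≤ 1 | L ≤ 11 |

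**3. What the rule does with such a scan.**

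- Read as SD, with nothing better: best response SD, confirmed and unconfirmed.
- Read as CR or PR and followed by PD or a non-evaluable assessment: SD under the confirmation table.
- Read as PD, as the only assessment: PD. This case is handled correctly.

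**4. Size.** Assume that the denominator is the planned number of response-evaluable patients. Each reclassified patient moves the SD row by 1/56 = 1.8 points (resistant cohort) or 1/48 = 2.1 points (sensitive cohort), and by more within a combination-partner column. The number of such patients is not in the documents and cannot be derived from them; the range starts at zero.

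**5. What does not move.** SD for 16 weeks needs SD at the end of Cycles 2 and 4, and SD for 24 weeks needs Cycle 6 as well (SAP 7.8.1 and 7.8.2). The exception tables for confirmed response are tied to the same scans. ORR counts only CR and PR. The futility rules (SAP 7.12) use CBR-16 alone. None of these depends on an SD reading before Day 54.

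**The case against.** The strongest reply is that the note is literally correct. It speaks of the first protocol scan, and the Schedule of Events marks no scan at EOT. Protocol 7.7 sends EOT procedures back to that schedule. Footnote (f) only says when a scan is not needed, and footnote (g) hangs on the three-monthly follow-up cell, where a scan would usually come well after week 8. The Protocol also refers to the treatment period, and a scan 30 to 40 days after the last dose is arguably outside it.

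Much of this stands. A reader might infer that the SAP's premise is simply false; it is not, because the EOT scan is implied and not scheduled. The reply does not close the gap, though. The SAP's window runs past treatment until subsequent therapy, and footnotes (f) and (g) together foresee scans in patients who stop without progression. Even on the narrower Protocol wording, an unscheduled scan during treatment and before Day 54 would count.

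Table 7.a has a row for "Disease progression documented between scheduled visits", from which one might infer that the SAP expects early SD readings. It covers progression for PFS only, so it gives little support.

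A reader might also infer that the efficacy result is inflated, or that early intolerance will be presented as disease control on a material scale. The documents support neither. The endpoints with a decision rule are untouched, no disease-control rate is built on the plain SD row, SD-16 and SD-24 stand in the same table, and SD duration is listed by patient. Nothing in the documents supports any particular number of affected patients.

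Finally, the SAP says that a week-8 scan satisfies the minimum, not that the minimum is 8 weeks. That is fair. A shorter minimum would narrow the group, as the 6-week line of the table shows, without removing it.

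**Conclusion.** The point holds as a gap in one descriptive derivation. Followed as written, SAP 7.8.3 can report SD on the strength of a scan taken before the earliest compliant Cycle 2 scan, because the reason for waiving the minimum does not cover every assessment that the rule admits. The effect is confined to the SD category of the best-response table, confirmed and unconfirmed, and the listing of SD duration. Its size is 1.8 or 2.1 points per patient, for an unknown number of patients that may be zero.

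This rests on three assumptions: that some early stoppers are scanned at EOT or off schedule, that those scans are read as SD or as a CR or PR that is not confirmed, and that Study Day 54 is the right cut-off. The last is taken from the SAP's own 8-week premise less the Protocol's window, since neither document states a numeric minimum for SD. The change is worth making because it is cheap and makes the derivation do what the note already assumes.

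**What to change.** Replace the note in SAP 7.8.3 with:

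> SD as best response (unconfirmed or confirmed, including unconfirmed CR or PR converted to SD) requires an assessment of SD or better on or after Study Day 54 (end of Cycle 2 less the 2-day window; first dose = Study Day 1). If the only SD-or-better assessments are earlier, best response is PD when PD follows, otherwise not evaluable (reported under Unable to Assess, with that category's definition extended to cover this case).

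Two details matter. The limit should be written as a study day and not as days elapsed: a requirement of at least 54 days after first dose would reject a compliant scan on Study Day 54, which is 53 days after it. The definition of Unable to Assess also has to be widened, because the SAP now allows that category only when it is the sole assessment available.

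The cost is one SAP sentence, one widened definition and one date check in the program. If no patient has an early scan, no result changes. If some do, the reported SD rate falls slightly.

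### Duration of response and of stable disease have no stop at subsequent anticancer therapy, unlike best overall response and PFS in the same SAP

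*SAP*

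**What the plan says.** Four rules in the SAP bear on this.

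- **DOR (SAP 7.8.3).** The clock runs from the first CR or PR "until progressive disease or until the last response assessment if there is no progressive disease". The analysis is more than a listing: "For phase 2 the Kaplan-Meier method will be used to analyze the DOR", with quartiles and confidence intervals.
- **Duration of stable disease (SAP 7.8.3).** "The duration of SD is the number of days from cycle 1 day 1 until progressive disease", again with the last response assessment as the fallback. This is listed only.
- **Best overall response (SAP 7.8.3).** Confirmed and unconfirmed versions are both defined as "The best response after the first dose of study drug until subsequent therapy".
- **PFS (SAP 7.8.2, Table 7.a).** If another therapy starts before progression, PFS is censored at the "Date of last adequate assessment prior to the start of subsequent therapy".

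On scanning, footnote (g) of the protocol's Schedule of Events covers follow-up. "For those patients who discontinue MLN0128 for any reason other than radiographic disease progression", CT or MRI should be done to look for progression, and the schedule shows this every 3 months. Footnote (b) says patients enter follow-up at the end-of-treatment visit, which the start of a new anticancer therapy can trigger. Protocol 7.10 collects the start of another anticancer therapy.

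**The concern.** The window that decides whether a patient is a responder closes at new therapy, and so does the PFS window. The window that decides how long the response lasted does not. Restricting DOR to patients with a best response of CR or PR fixes who enters and when the clock starts, but not when it stops.

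Two things are at stake. First, DOR will be read as the durability of response to MLN0128 plus endocrine therapy, and months spent on a different regimen do not measure that. Second, the outputs may not reconcile. Under a shared stopping rule DOR must be shorter than PFS, because it starts later and ends on the same date. Under the rules as written, a patient's DOR can be longer than her PFS, and can be an event where her PFS is censored. Responders may be few: the cohorts are capped at 56 and 48 response-evaluable patients, so one or two such cases could move a Kaplan-Meier quartile.

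**Working it through.** The plan gives no DOR figure to reproduce. The check has three parts: whether the situation can arise, what it does to one patient, and what it might do to a summary.

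**1. Can scans after new therapy exist?** No protocol text ends scanning at new therapy. Follow-up can begin at that moment and includes imaging every 3 months for patients who stopped without radiographic progression. Table 7.a's subsequent-therapy row would also have little to do if no later assessments were expected. Such scans are therefore possible, although no sentence expressly requires them.

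**2. One patient (dates assumed).** Response at week 8 (end of Cycle 2), last scan before new therapy at week 16 (end of Cycle 4), new therapy at week 20, progression at week 60. PFS is counted from first dose, using "date of first dose of MLN0128 + 1)/30.4375".

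- PFS, Table 7.a: censored at day 16 × 7 = 112; 112 / 30.4375 = 3.7 months.
- DOR as written: event after (60 − 8) × 7 = 364 days; 364 / 30.4375 = 12.0 months.
- DOR under the PFS convention: censored after (16 − 8) × 7 = 56 days; 56 / 30.4375 = 1.8 months.

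Progression is not needed for the mismatch. Take new therapy on day 130 and one follow-up scan 91 days later (day 221) without progression. DOR as written is 221 − 56 = 165 days, or 5.4 months, against the same PFS of 3.7 months.

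**3. Effect on the summary (all inputs assumed).** Let time from response to progression be exponential with median 5 months, so λ = ln 2 / 5 = 0.1386 per month. Let switching be independent, with hazard s = λq/(1 − q), so that a share q of responders switches before progressing. After the switch, the progression hazard is hλ. The DOR curve as written is then

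S(t) = exp(−(λ+s)t) + s[exp(−hλt) − exp(−(λ+s)t)] / (λ + s − hλ).

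Solving S(t) = 0.50 and S(t) = 0.25, in months:

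| Post-switch hazard ratio h | Median, q = 20% | Median, q = 40% | Upper quartile, q = 20% | Upper quartile, q = 40% |
|---|---|---|---|---|
| 2.0 | 4.7 | 4.3 | 9.1 | 8.1 |
| 1.5 | 4.8 | 4.6 | 9.4 | 8.8 |
| 1.0 | 5.0 | 5.0 | 10.0 | 10.0 |
| 0.7 | 5.1 | 5.4 | 10.6 | 11.4 |
| 0.5 | 5.3 | 5.7 | 11.2 | 13.2 |

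Against the true median of 5.0, the range is about −13% to +14%. It is zero when the next therapy has the same progression hazard.

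**The case against.** The strongest objection is that censoring at new therapy has a bias of its own. It assumes that switching is unrelated to prognosis. Yet SAP 7.8 lists symptomatic deterioration at response assessments for phase 1b, so decline without RECIST progression is foreseen. In a deliberately extreme case, a share q of responders switches after 80% of its time to progression and is censored there. The Kaplan-Meier median then solves 4 ln[(1 − q)exp(0.25λt) + q] = ln 2, which gives 6.1 months at q = 20% and 7.9 months at q = 40%, against a true 5.0. This stands as a caution: whether to follow patients through new therapy is a choice of what to estimate, and censoring does not guarantee less bias. But the SAP has already accepted this assumption for PFS, and the case for alignment rests on consistency.

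A second objection is that the PFS prose does not mention subsequent therapy either, and that a programmer might carry the best-response window over to DOR. That is possible. However, Table 7.a states the rule explicitly for PFS, and nothing extends it to DOR, so two programmers could reach different results.

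A third is that footnote (g) says nothing about scans after a new therapy. That is correct, and the point needs only that such scans are possible.

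**Conclusion.** The inconsistency is real and minor. As written, DOR and duration of stable disease can include time on a later regimen, while best overall response and PFS cannot. A patient's DOR can then exceed her PFS.

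A reader might infer that DOR will be inflated because the next treatment's benefit is credited to MLN0128. The documents do not support that. They give no expected number of responders who switch before progression and are scanned later. They also give no basis for assuming that the next therapy controls disease better than the study regimen. The range of 4.3 to 5.7 months rests on an assumed 5-month exponential median, 20-40% independent switching, and hazard ratios of 2.0 to 0.5. The single-patient example shows a mismatch between two rules and does not measure bias.

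Nor does the point reach the trial's main conclusions. DOR is an additional, descriptive SAP endpoint and is absent from the secondary endpoint lists. Duration of stable disease is listing-only. CBR-16, its interim and final thresholds, ORR, PFS and OS do not use either rule. How DOR treats death without progression is a separate question.

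**What to change.** Add one sentence to SAP 7.8.3, covering both DOR and duration of stable disease: if another anticancer therapy starts before documented progression, the duration is censored at the last adequate assessment before that therapy began, as in the subsequent-therapy row of Table 7.a. Best response, PFS and the two durations then share one window.

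No new data are needed, because the protocol already collects the start of another anticancer therapy. The cost is more censored DOR times in what may be a small group, so wider intervals. That censoring may be informative if patients switch because of clinical decline, and the report should say so, as it would for PFS.
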